16.1.2. Methods of Analysis

Continuous variables will be summarized using descriptive statistics (number of subjects [n], mean, standard deviation [SD], median, minimum, and maximum) by treatment group, and categorical variables will be presented using frequency distributions by timepoint and treatment group. Point estimates and 90% CIs will be provided where applicable.

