16.1.2.1. Analysis of the Primary Endpoint

The primary endpoint is the change of MCCB Working Memory Domain score from baseline to Week 12. An MMRM model will be used as the primary analysis to analyze change from baseline in Working Memory Domain score using fixed effects of treatment, visit, treatment by visit interaction, baseline Working Memory Domain score, baseline Working Memory Domain score by visit interaction, and region.

[figure not shown]
In the analysis of the primary endpoint, missing data will be assumed to be missing at random (MAR). An unstructured variance-covariance structure will be used to model the within patient measurements variability. If this analysis fails to converge, other structures will be tested such as heterogeneous autoregressive, heterogeneous compound symmetry, or heterogeneous Toeplitz. The variance-covariance structure that results in the smallest Akaike information criterion will be used. The Kenward-Roger approximation will be used to estimate the denominator degrees of freedom. Sensitivity analyses will be carried out to assess the robustness of primary analysis to deviation from the MAR assumption. Details of sensitivity analyses and assumptions for different missing patterns will be described in the SAP.

CONFIDENTIAL

The information contained herein may not be used, disclosed, or published without the written consent of
Biogen MA Inc.

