16.6. Sample Size Considerations

Fifty-one subjects per treatment group will have approximately 80% power to detect a true mean difference of 3.5 in change from baseline MCCB Working Memory Domain score to Week 12 between the treatment and placebo groups. With the assumed drop-out rate of 30%, 73 subjects are required from each group to maintain the 80% power. This power calculation is based on a 2-sided *t*-test assuming equal variance with a final significance level of 0.1, and an SD of 7. The statistical software EAST 6.3® is used for sample size calculation. The sample size may be re-estimated based on blinded data review and evolving development of this study.

CONFIDENTIAL

The information contained herein may not be used, disclosed, or published without the written consent of
Biogen MA Inc.

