3. SAMPLE SIZE JUSTIFICATION

The protocol states that:

Fifty-one subjects per treatment group will have approximately 80% power to detect a true mean difference of 3.5 in change from baseline MCCB Working Memory Domain score to Week 12 between the treatment and placebo groups. With the assumed drop-out rate of 30%, 73 subjects are required from each group to maintain the 80% power. This power calculation is based on a 2-

sided *t*-test assuming equal variance with a final significance level of 0.1, and a standard deviation of 7. The statistical software EAST 6.3® is used for sample size calculation. The sample size may be re-estimated based on blinded data review and evolving development of the study.

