4. STATISTICAL ANALYSIS METHODS

4.1 General Considerations

This statistical analysis plan (SAP) describes the planned analyses for this phase 2 study evaluating the primary, secondary [REDACTED] objectives. This SAP also covers the planned interim and final analyses, and therefore there is no separate SAP for the interim analysis.

Data listings will be provided by treatment group, visit, and subject, if applicable. Summary statistics and statistical analyses will only be presented for data where detailed in this SAP. For continuous data, summary statistics will include the arithmetic mean, arithmetic standard deviation (SD), median, minimum (Min), maximum (Max) and n; for log-normal data the geometric mean and geometric coefficient of variation (CV) will also be presented. For categorical data, frequency count and percentages will be presented. Data listings will be provided for all subjects up to the point of withdrawal, with any subjects excluded from the relevant population highlighted. Summary statistics and statistical analyses will generally only be performed for subjects included in the relevant analysis population.

Data will be summarized and presented by treatment group, defined in Table 1. Data will be listed by treatment group. Exposure to study medication will be tabulated by treatment group.

Unless stated otherwise, baseline data are defined as the data collected prior to the time and/or on the day of the first dose, which is usually the same day as the Day1/Baseline visit. If data are not available on Day 1 for safety assessment, the measurements recorded up to 3 days prior to first dose (i.e. Day -3) will be used as baseline. For efficacy assessments, the Day1/Baseline visit may be performed over 2 days, i.e., on Day 1 and Day 2. Therefore, an assessment performed on the second day of visit Day1/Baseline (i.e., Day 2), will be used as baseline if not already performed on the first day of visit Day1/Baseline (i.e., Day 1). If there is more than one value on/before the day of the first dose, the non-missing value closest to and prior to the first dose will be used as the baseline value

Unless stated otherwise, all statistical tests will be 2-sided with statistical significance level of 0.10.

The statistical software, SAS 9.4®, will be used for all summaries and statistical analyses.

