The change from baseline will be summarized by treatment group at each post-baseline visit. A mixed model repeated measures (MMRM) model will be used as the primary analysis to analyze change from baseline of the endpoint of interest, using fixed effects of treatment group, study visit, study visit-by-treatment interaction, baseline value of the endpoint, and baseline-by-visit interaction. Region (stratification factor for randomization) will be included as a fixed effect but may be omitted in the case that the model fails to converge. An unstructured covariance matrix will be used to model the within-patient variance-covariance errors. If the unstructured covariance matrix results in a lack of convergence, the following structures will be used in order: heterogeneous Toeplitz (TOEPH), heterogeneous compound symmetry (CSH), antedependence (ANTE1), heterogeneous autoregressive (ARH1), autoregressive (AR1) and compound symmetry (CS). The first covariance structure yielding convergence will be used. If a structured covariance is used, the empirical “sandwich” estimator of the standard error (SE) of the fixed effects parameters will be used to deal with possible model misspecification of the covariance matrix. The Kenward-Roger approximation will be used to estimate the denominator degrees of freedom. The primary treatment comparison is BIIB104 treatment group versus placebo at the end of Week 12. In the primary analysis, missing data are assumed to be missing at random (MAR) [Rubin 1976]. To account for the interim analysis at the time of the final analysis, the median unbiased estimate of the primary treatment effect will be calculated as a supporting analysis.

However, for UPSA-Bi and SCoRS, which only have assessments at baseline and at Week 12, the primary analysis will be based on subjects who have both baseline and Week 12 assessments. An analysis of covariance (ANCOVA) model will be applied adjusting for treatment group and baseline value of the endpoint (UPSA-Bi or SCoRS, respectively).

Sensitivity analysis: Reference-based multiple imputation approach

The following sensitivity analysis will be performed to assess the robustness of the primary analysis with respect to deviation from the MAR assumption. All sensitivity analyses will be conducted for the ITT population.

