Intermittent (non-monotonic) missing data will be imputed based on the MAR assumption and with a multiple imputation model using Markov chain Monte Carlo (MCMC) method within each treatment group. The imputation models will include baseline value and the values at each post-baseline week for the endpoint of interest. The MCMC method in the PROC MI procedure in SAS will be used with a single chain, with a burn-in of 1000, and a thinning of 100 and non-informative priors for all parameters.

Reference-based multiple imputation (MI) approach will be used to impute missingness post treatment discontinuation and consider a missing not at random (MNAR) mechanism for monotonic missing data. Imputed values in the reference group (placebo) will assume MAR. Imputed values in the BIIB104 treatment groups will be based on data from the placebo group using sequential regression MI model. Each sequential regression model (i.e., for imputation of values at a given week) will include visits of endpoint. This approach assumes no sustained benefit of BIIB104 after discontinuation of study treatment and limits post-discontinuation effects to that of placebo.

Two hundred imputations will be performed and from each of the imputed datasets, least square (LS) mean differences from placebo and their standard errors will be combined using Rubin's method [Rubin 1987]. PROC MIANALYZE procedure is used to produce a pooled LS mean estimate of treatment difference at Week 12, its 95% CI, and a pooled p-value.

Complementary Analysis: include data after intercurrent events

This is a complementary analysis to the primary and sensitivity analyses (efficacy estimand) for the ITT population. All observed data including those collected after intercurrent events [ICH E9 (R1) Addendum 2017], i.e. premature discontinuation of the study treatment, will be included. The estimate of this analysis reflects the treatment effect of BIIB104 seen as actually taken. This is considered [*de facto*] effectiveness estimand. When all data after intercurrent events are included, the same MMRM model as the primary analysis will be applied. In this complementary analysis, missing data are assumed to be missing at random [Rubin 1976].

The per-protocol analysis will be done using the same model as the primary analysis and applying in the per-protocol population.

Responder Analysis: threshold determined using distribution-based method

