4.4.2.2 Sensitivity Analysis

Reference-based multiple imputation approach will be performed on the primary endpoints using the methods as described in [Section 4.4.1](#).

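### The reference-based imputation result is to be reported with a 95% CI in a trial that tests at two-sided 0.10 and plans 90% CIs, and no reason is given

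*SAP*

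**What the plan says.** SAP 4.4.1, in the part on the reference-based multiple imputation sensitivity analysis, combines 200 imputed datasets by Rubin's method and has PROC MIANALYZE produce "a pooled LS mean estimate of treatment difference at Week 12, its 95% CI, and a pooled p-value".

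The other statements of level in the two documents are these:

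- SAP 4.1, as the default: "all statistical tests will be 2-sided with statistical significance level of 0.10".
- Protocol 16.6, on sample size: "assuming equal variance with a final significance level of 0.1, and an SD of 7". SAP 3 repeats this level.
- Protocol 16.1.2, and the Synopsis in the same words: "Point estimates and 90% CIs will be provided where applicable".

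On the role of the analysis, SAP 4.4.1 states: "The following sensitivity analysis will be performed to assess the robustness of the primary analysis with respect to deviation from the MAR assumption". SAP 4.4.2.2 applies it to the primary endpoint and SAP 4.4.3 to the key secondary endpoints. Protocol 16.1.2.1 leaves the specification to the SAP: "Details of sensitivity analyses and assumptions for different missing patterns will be described in the SAP".

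**The concern.** The sensitivity analysis will be read beside the primary analysis, because its purpose is to show whether the primary conclusion survives a departure from missing at random. Under Protocol 16.1.2 the primary interval would be at 90%. With the companion interval at 95%, part of any widening comes from the confidence level and not from the imputation assumption.

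The two levels can also give different readings. A reader who checks whether the interval covers zero would be applying a 0.05 test, while SAP 4.1 has the pooled p-value judged at 0.10. For some results the printed interval and the trial's own significance rule would appear to disagree.

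**Working it through.** **1. Does the design rest on 0.10?** Inputs from Protocol 16.6: difference 3.5, SD 7, two-sided alpha 0.1, power about 80%, 51 evaluable per group, 30% dropout, 73 randomized per group.

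- Normal approximation: n = 2 × (1.645 + 0.842)² × 7² / 3.5² = 49.5, so 50 per group.
- Exact (noncentral) t-test at alpha 0.10: power is 79.9% with 50 per group and 80.6% with 51. The stated 51 is reproduced.
- Dropout: 51 / 0.70 = 72.9, so 73. Reproduced.
- At alpha 0.05, 51 per group would give only 70.6% power.

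The design therefore rests on 0.10, and the matching interval level is 1 − 0.10 = 90%.

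**2. How much wider is the 95% interval?** For a fixed estimate and standard error (SE), the width ratio is the ratio of critical values.

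| Degrees of freedom | 95% value | 90% value | Ratio |
|---|---|---|---|
| normal limit | 1.960 | 1.645 | 1.192 |
| 200 | 1.972 | 1.653 | 1.193 |
| 100 | 1.984 | 1.660 | 1.195 |
| 50 | 2.009 | 1.676 | 1.198 |

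The SAP does not state the pooled degrees of freedom. With 200 imputations, Rubin's 1987 formula gives at least 200 − 1 = 199, which points to a ratio of about 1.19. The lower rows would matter only if a small-sample adjustment were used, and the SAP mentions none.

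**3. When do the two levels read differently?** The 95% interval touches zero at p = 0.05 and the 90% interval at p = 0.10. They disagree about zero only between those values. An example that needs no assumed SE is p = 0.07, where the estimate is 1.812 SE from zero (normal):

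- 90% CI: 1.812 ± 1.645 = 0.17 to 3.46 SE, which excludes zero.
- 95% CI: 1.812 ± 1.960 = −0.15 to 3.77 SE, which covers zero.

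At 100 degrees of freedom the intervals are 0.17 to 3.49 SE and −0.15 to 3.82 SE, with the same reading.

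**4. What does this look like at the planning values?** This step is illustrative. It uses the complete-data t-test SE, because the documents do not give the pooled imputation SE.

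- SE = 7 × √(2/51) = 1.386.
- Half-width with 100 degrees of freedom: 1.660 × 1.386 = 2.30 points at 90%, and 1.984 × 1.386 = 2.75 points at 95%.
- An observed benefit between 2.30 and 2.75 points would fall in the discordant band.
- If the true difference is 3.5, the chance that p lies between 0.05 and 0.10 is 80.6% − 70.6% = about 10 percentage points.

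**5. Is there a stated reason for 95%?** SAP 4.4.1 names no different test level for this analysis. It also makes no multiplicity adjustment, so that cannot explain a stricter level. The 95% is the only confidence level in the visible SAP text, and the SAP names none for the primary mixed model or for the ANCOVA.

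**The case against.** The best defence is that no rule is broken. The protocol's sentence on 90% intervals is general and qualified, the protocol delegates the details of sensitivity analyses to the SAP, and the 0.10 level in SAP 4.1 governs tests and not interval width. A 95% interval is a valid summary of uncertainty and need not mirror the test. That much is right: this is an unexplained mismatch of levels and not a breach of an explicit requirement.

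Second, the reader already has what is needed. The pooled p-value is in the same sentence, and a 90% interval can be rebuilt from the estimate and the 95% limits. No decision rule in the visible text uses this interval, and robustness is judged mainly by how far the estimate moves, which the level does not affect. This limits the weight of the point but does not remove it: readers would have to repair a display that the SAP can set correctly in advance.

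Third, the 90% level for the primary interval is inferred from the protocol's general sentence, because the SAP is silent. That is also true. A Week 12 treatment difference is nevertheless the most natural place for that sentence to apply.

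**Conclusion.** The point holds and is minor. The sensitivity interval in SAP 4.4.1 is at a level that does not match the trial's test level or the protocol's general interval level, and the visible text does not explain why. The interval is about 19% wider than its 90% counterpart. The reading against zero changes only when the pooled p-value lies between 0.05 and 0.10.

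The estimate, its standard error, the p-value, the primary test, type I error, power and the futility rule are unchanged. The width figure assumes the same estimate and standard error at both levels. The comparison with the primary interval assumes that it is reported at 90%, as Protocol 16.1.2 indicates.

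**What to change.** In the PROC MIANALYZE sentence of SAP 4.4.1, replace 95% with 90% and set alpha to 0.10 for every endpoint that uses this analysis. If a 95% interval is also wanted, label it as additional. It would help, though it is optional because Protocol 16.1.2 already covers it, to state 90% in the SAP for the mixed-model and ANCOVA differences, so that a programmer working from the SAP alone does not carry the 95% over to them.

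The cost is one number in the SAP and one programming option. Data, tests and sample size do not change.

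### The complementary analysis is labelled as the effect as actually taken, but its MAR assumption for uncollected off-treatment values pulls it toward the primary result if benefit fades and follow-up is incomplete

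*SAP*

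**What the plan says.** SAP 4.4.1 defines three relevant analyses of the Week 12 change.

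- **Primary.** Data are censored when a subject stops study treatment, and an MMRM is fitted under MAR. The SAP calls this the de jure efficacy estimand.
- **Sensitivity.** Values missing after discontinuation are imputed from placebo data by sequential regression under MNAR, on the premise that no benefit is sustained off drug. The SAP groups this with the primary analysis under the efficacy estimand.
- **Complementary.** All observed data are used, including those after discontinuation, with the same MMRM as the primary analysis. The target is stated without qualification: "The estimate of this analysis reflects the treatment effect of BIIB104 seen as actually taken". For what remains missing: "In this complementary analysis, missing data are assumed to be missing at random".

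SAP Table 5 assigns the complementary analysis under MAR to the key secondary endpoints as well.

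On follow-up, Protocol 10.1 asks everyone who stops treatment to stay in the study and continue visits. No expected retention rate is given. The only related figure is in Protocol 16.6: "With the assumed drop-out rate of 30%, 73 subjects are required from each group". That figure is not divided into stopping treatment and leaving the study.

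**The concern.** An as-taken estimand needs the outcomes that discontinuers actually have after stopping. Where those outcomes are observed, the complementary analysis uses them. Where they are not, an MMRM under MAR fills them in from the fitted same-arm trajectory. Nothing in the model separates on-treatment from off-treatment records, and most same-arm subjects at Week 12 are likely to be on drug. An unretrieved discontinuer is therefore credited largely with an on-drug outcome. For that subject the complementary and primary analyses make nearly the same assumption under opposite labels.

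What is at stake is interpretation. The two results would be read side by side, and agreement between them would be taken as evidence that discontinuation matters little. Part of that agreement could come from the missing-data assumption and not from the data. No analysis described in the SAP combines observed off-treatment data with a non-MAR assumption for the unretrieved remainder, which is the combination the stated estimand calls for if benefit fades after stopping.

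**Working it through.** **1. The plan's own figures.** The inputs are a "true mean difference of 3.5 in change from baseline MCCB Working Memory Domain score to Week 12", tests "with a final significance level of 0.1, and a standard deviation of 7" (SAP 3), two-sided (SAP 4.1), and "Fifty-one subjects per treatment group will have approximately 80% power". The normal approximation gives n = 2 × (1.645 + 0.842)² × (7/3.5)² ≈ 49.5, so 50 per group. Exact t-test power is 79.9% at 50 and 80.6% at 51. Inflating for drop-out, 51/0.70 = 72.9, so 73 per group and 3 × 73 = 219. The sample size reproduces.

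**2. Closed form.** Let d be the share stopping treatment, r the share of those with Week 12 data, and assume no effect remains off drug.

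- True as-taken effect = 3.5(1 − d)
- MMRM under MAR ≈ 3.5(1 − d)/(1 − d + d·r), because the missing values take the mean of the observed same-arm mixture

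The documents do not say that 30% stop treatment; d = 0.30 is an assumption borrowed from the drop-out figure. The true effect is then 3.5 × 0.70 = 2.45.

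| Retrieved share r | Planned analysis | Excess over 2.45 |
|---|---|---|
| 0% | 2.45/0.700 = 3.50 | 1.05 |
| 25% | 2.45/0.775 = 3.16 | 0.71 |
| 50% | 2.45/0.850 = 2.88 | 0.43 |
| 75% | 2.45/0.925 = 2.65 | 0.20 |
| 100% | 2.45/1.000 = 2.45 | 0 |

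With d = 20% the true value is 2.80 and the estimate at 50% retrieval is 3.11. With d = 10% they are 3.15 and 3.32.

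**3. If half the effect persists off drug.** True effect = 0.7 × 3.5 + 0.3 × 1.75 = 2.975. With no retrieval the planned analysis still gives 3.50, so the largest gap is 0.525. If the whole effect persists, the true value is 3.5 and there is no gap.

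**4. Simulation check.** An unstructured MMRM at Weeks 2, 6 and 12 was fitted to 400,000 simulated subjects per scenario (simulation error about 0.02 to 0.03). Within-subject correlation was 0.5 or 0.7, and discontinuation was either random or dependent on the last score. With random stopping and no off-drug effect the estimates were 3.47–3.50, 3.15–3.20, 2.88–2.89, 2.63–2.68 and 2.45–2.46 at 0, 25, 50, 75 and 100% retrieval, against a true value of 2.41–2.47. With score-dependent stopping (29% stopping) the true value was 2.57–2.63 and the estimate at 50% retrieval was 2.95–3.02. Across all scenarios, including half the effect retained, the share of the gap back to the de jure value was 100%, 68–72%, 42–44%, 19–21% and 0%.

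**5. How far the planned reference-based imputation would help.** It regresses on earlier visits, so earlier on-drug gains carry forward in part. Assume 10% stop in each of the three intervals between visits, and correlation 0.6 between any two visits. The imputed Week 12 effect is then:

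- 0 for those stopping before Week 2
- 0.6 × 3.5 = 2.10 for those with Week 2 only
- 2 × 0.6/1.6 × 3.5 = 2.625 for those with Weeks 2 and 6

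With no retrieval the estimate is 2.45 + 0.1 × (0 + 2.10 + 2.625) = 2.92. At 50% retrieval it is 2.45 + 0.05 × 4.725 = 2.69. Simulation gave 2.92 and 2.68. If benefit is lost at once, this removes a little over half of the no-retrieval gap. If half the effect persists, 2.92 is close to the true value of 2.975.

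**The case against.** A reader might infer that this analysis can never estimate the as-taken effect, or that it must match the primary result by construction. The documents do not support that. Protocol 10.1 plans follow-up after discontinuation, so zero retrieval is not the intended conduct. With complete Week 12 follow-up the analysis is on target, and at 75% the excess is about 0.2 point even if benefit vanishes at once.

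Four further points favour the plan:

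- **Size.** The gap depends on the loss of benefit, which is assumed. The standard error of a difference at 51 per arm is 7 × √(2/51) = 1.39, so an excess of 0.43 at 50% retrieval is modest beside sampling error.
- **Drop-out figure.** Equating the 30% with treatment discontinuation is an assumption.
- **Existing protection.** The placebo-based imputation will be reported for the primary and key secondary endpoints, which limits false reassurance.
- **Role.** The analysis is complementary, carries no stated decision rule, and declares its MAR assumption openly.

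These points limit the size and importance of the problem but do not remove the mismatch. Follow-up is requested, not assured: Protocol 10.2 withdraws subjects unable or unwilling to comply, and Protocol 11.3 allows withdrawal for poor dosing compliance. Early-termination assessments do not fill the gap, because under SAP Table 2 a visit before Day 71 is mapped by analysis day and not to Week 12. The placebo-based imputation is tied to the efficacy estimand and is not attached to this analysis.

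**Conclusion.** The concern holds as a mismatch between label and assumption, and its effect is a matter of degree. For off-treatment values that are not collected, MAR under the primary MMRM does not fit a de facto estimand. If benefit fades after stopping and follow-up is incomplete, the estimate is pulled toward the de jure value. With 30% stopping and immediate loss of a 3.5-point effect, the pull is about 1.05 points with no retrieval, 0.7 at 25%, 0.4 at 50%, 0.2 at 75% and none at 100%. It is at most about 0.5 point if half the effect persists and nil if all of it does.

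The stopping rate, the off-drug effect and the retrieved share are all assumptions; the documents fix none of them. Should every planned drop-out be a discontinuer without Week 12 data (51 of 73 observed), the two analyses would give essentially the same answer.

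The primary estimand, test and power are unaffected. This is a worthwhile and inexpensive correction, not a threat to the trial's main conclusion.

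**What to change.** In the complementary analysis of SAP 4.4.1 and Table 5:

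1. Keep all observed off-treatment data.
2. Impute values still missing after discontinuation with the reference-based multiple imputation already specified. Use retrieved discontinuers of the same arm instead if there are enough of them. At 30% stopping, 0.30 × 73 is about 22 per arm, so 50% retrieval leaves about 11, spread over three intervals. State the minimum number in advance.
3. Keep MAR for intermittent gaps only.
4. Report by arm the share of discontinuers with observed Week 12 data.
5. State that the reference-based method conditions on earlier on-drug visits, so it reduces the drift without fully removing it if benefit is lost at once (about 2.9 with no retrieval and 2.7 at 50%, against 2.45).

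The cost is one further run of imputation code already planned and a few sentences in the SAP; imputing from retrieved discontinuers would need new code. The interval may be wider and the estimate smaller.
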